Basic Attention and	Trail Making Test Part A*	Visuomotor Attention and Processing
Cognitive Bias	WAIS-IV Symbol Search	Speed
	WAIS-IV Digit Symbol	
	Approach-Avoidance Task	Attentional and Cognitive Biases

Verbal and Visual	Brief Visual Memory Test-R	Visuospatial learning and recall memory
Learning & Memory	Hopkins Verbal Learning Test–R*	Auditory learning and recall memory
Working Memory	WAIS-IV Arithmetic	Abstract Reasoning, Mental Calculation
	WAIV-IV Digit Span	Mental Tracking, Organization, Sequencing
	WAIS-IV Letter Numb Sequencing*	Mental Reorganization; Sequencing
Impulsivity and	Delis-Kaplan Color-Word Stroop Test	Inhibition of an over-learned response
Decision Making	Continuous Performance Task*	Sustained Attention, Vigilance, Inhibition
	Iowa Gambling Task	Decision-Making, Risk-taking
	Delay Discounting Task	Decision-Making, Reward Processing
Mental Flexibility	Wisconsin Card Sorting Task	Rule-Learning, Set-Shifting
	Delis-Kaplan Tower Task	Planning, Rule-Learning
	Trail Making Test Part B*	Speeded Set-Shifting

Measures: Alcohol Use

Alcohol Use. The Time-Line Follow-Back (TLFB) interview provides a calendar-guide of a targeted time period to help participants retrospectively record the number of standard drinks consumed on each day. The TLFB procedure has demonstrated good reliability and validity in past work across diverse samples (Sobell & Sobell, 1992) and data will be used to calculate the primary drinking outcome variable, average drinks per drinking day (the number of drinks consumed divided by the number of drinking days). The TLFB will be administered in an interview format at each study visit.

Breath Alcohol Concentration (BrAC). The *Intoximeter Alco-Sensor IV* (Intoximeters Inc.) instrument will be used to measure BrAC at each visit to ensure that subjects are not acutely intoxicated.

Measures: Functional Status and PTSD Symptom Severity.

Drug User Quality of Life Scale (DUQLS; Brogly et al., 2003). The DUQLS is a culturally relevant tool for assessing quality of life and satisfaction among individuals with SUD. Participants are also asked to classify each of the 22 life areas (including SUD treatment) as "important" or "unimportant" to them. Reponses on the DUQLS can be summed to generate an overall quality of life score as well as sub-scores that reflect quality of life in life areas that are important and unimportant to the participant.

Psychosocial Functioning: The 80-item Inventory of Psychosocial Functioning (IPF; Marx et al., 2009), was developed among Veterans to assess level of functional impairment. The IPF includes self-report and behavioral indices that assess current psychosocial functioning across 7 domains. Domain scores are summed to yield a total score for psychosocial functioning.

PTSD Symptoms. The PTSD Checklist – Military Version (PCL-M; Weathers et al., 1993) is comprised of 17 items that correspond to the 17 DSM-IV (APA, 2000) symptoms of PTSD. The PCL-M provides an index of global PTSD symptom severity and will be administered throughout the study. The 20-item PCL-M for DSM-5 is being piloted (Weathers et al., 2012; National Center for PTSD) and will be incorporated upon its release.

Measures: Potential Covariates and Secondary Measures. Potential covariates will be included in an initial analytic model for Stage 2 if deemed necessary (e.g., not evenly stratified through randomization).

Non-Alcohol SUD Diagnoses and Use. Non-alcohol SUD and other Axis-I psychiatric disorders will be determined at baseline with the SCID-I (First et al., 1995), modified for DSM-5. TLFB interview procedures (see above; Sobell & Sobell, 1992) will be used to assess patterns of non-alcohol substance use.

Attention Deficit Hyperactivity Disorder. Conner's Adult ADHD Diagnostic Interview for DSM-IV (CAADID; Epstein et al., 2001) will be administered at baseline to specifically asses for ADHD.

Alcohol Dependence Severity. The 10-item Alcohol Use Disorder Identification Test (AUDIT; Saunders et al.,1993) will be administered at each visit to assess alcohol dependence and harmful and hazardous drinking. Prescription Medication Use: All prescription medications will be documented at baseline. Changes in prescription medication use and dose will be tracked using self-report and the VA electronic medical record.

Training adherence and performance. Number of hours completed and aggregated performance indices (i.e., training effort and dose) will be recorded directly from the computer programs each training week.

AUD and PTSD Treatment: Information on past and concurrent AUD and PTSD treatment will be gathered at each study visit using the Psychosocial Treatment Interview (PTI) (Steketee et al., 1997).

Depression and Anxiety: General levels of depression and anxiety will be measured at baseline and each study week with the 64-item Inventory of Depression and Anxiety Symptoms (IDAS; Watson et al., 2007).

Table 2. Overview of assessments to be administered

Clinical Assessments and Procedures	Phone Screen	Screening Visit	Baseline Assessment	Each Study Week	Week 3	Week 6 Post- Training	3 or 6 Month Follow up
Inclusion/Exclusion							_
Study Explanation	Χ						
Demographic Information	Х	Χ					
SCID-I – AUD		Χ					
CAPS – PTSD Interview		Χ					
Cognitive Screening-Table 1*		Х					
WTAR – Premorbid IQ Proxy		Х					
MMSE – Dementia Screen		Х					
DoD Severe TBI Screen		Χ					
Outcomes							
(S1) Acceptability/Usability Measures and Testing			X (orientation)		Х	X	
(S1) Interviews and/or Moderated Focus Groups					X	X	
Neuropsych Assessment			X			Χ	Χ
TLFB – Alcohol Consumption			X	Χ		Χ	X
DUQLS; IPF - Functional			X			Χ	X
PCL – M – PTSD symptoms			X	Χ		Χ	X
Potential Covariates, Second	lary Meas	ures					
TLFB - non-alcohol sub use				Χ		Χ	Χ
SCID-I (Axis 1 disorders)			X				
CAADID – ADHD			X				
AUDIT – AUD Severity			X	Χ		Χ	X
Training Adherence				Χ			
IDAS – Depression/Anxiety			X	Χ		Χ	Χ
PTI - Past/Current Treatment	Χ		X	Χ		Χ	X
Prescription Medication	Χ		X	Χ		Χ	Χ
Other							
Collateral h	istory fron	n medical re	cord/outpatien	t SUD tr	eatmen	t team as r	necessary
Study Informed Consent		Χ					
Randomization Checklist			Х				
Training Check-in Meetings				Х			
Breath Alcohol Concentration		X	Χ	Х		Χ	Χ

2a.3.j. Planned Data Analysis.

Missing Data. All laboratory-based measures will be reviewed for completeness immediately following collection, prior to the participant's dismissal. Despite our intensive protocol to limit participant attrition, we do expect missing data over the course of this study (i.e., 30%) and have adjusted our recruiting sample accordingly. To minimize the impact of missing data from incomplete protocols, we will use model-based multiple imputation procedures appropriate for longitudinal research described by Schafer and Graham (2002) and conduct analyses to evaluate the sensitivity of the results to model assumptions (Little & Rubin, 1987).

Power Analysis. Analyses are powered based on a sample size that accounts for 30% attrition in both study stages (i.e., Stage 1, n = 14; Stage 2; n = 90). For Stage 1, the primary aim is to examine usability, acceptability and feasibility of both the cognitive training and the computer-game control. The proposed recruitment sample size (n = 20; 10 training, 10 control), which allows for up to 30% attrition, should be adequate given that previous studies have found that 3-7 test users is sufficient to identify the majority of usability problems (Nielsen & Landauer, 1993). This sample size will also allow us to conduct a sufficient number of in-depth multi-modal assessments to identify acceptability concerns. For Stage 2, we conducted a

power analysis to determine the needed sample size to analyze the primary hypothesis under Aim 2 while balancing Type I and Type II error rates. Three sources of information were considered: (1) Existing empirical work involving cognitive training among AUD populations has established medium to large effect sizes for cognitive outcomes (partial η^2 = .1, Rupp et al., 2012; Cohen's d = .42, .64, Goldstein et al., 2005; partial η^2 = .27. Houben et al., 2011a), (2) [name] observed an effect size of d = .66 for Global Cognition in her recently completed study among individuals with schizophrenia comparing a cognitive training intervention to a computer-game control condition (both of which will be employed in the proposed study); (3) The magnitude of change in neuropsychological test performance required to detect a clinically significant and meaningful effect (e.g., Temkin et al., 1999). Together, the described considerations led to a sample size recruitment estimate of 128 participants (64 training, 64 control) for Stage 2, that will allow for up to 30% attrition. Calculations are based on the most conservative test of group mean differences, a 2-tailed independent samples t-test. Accounting for 30% attrition, a final sample size of 90 will provide an estimated power of 80% to detect a medium effect (d = .60) of cognitive training at follow-up (that is also within the range of observed effect sizes in other cognitive training studies with AUD) at an alpha level of .05. Given that previous cognitive training studies in AUD samples have reported medium sized effects for alcohol outcomes (partial η^2 = .16; Houben et al., 2011a; partial η^2 = .12; Rupp et al., 2012; partial η^2 = .1; Eberl et al., 2013) and psychological well-being (partial η^2 = .12; Rupp et al., 2012), the proposed sample size should also be adequately powered to test Aim 2 secondary hypothesis b (alcohol, PTSD and quality of life outcomes).

The normality and range of data distributions will be examined and appropriate data transformations will be made when necessary. The data will also be screened for violations of assumptions underlying the statistical tests described below and when necessary, models will appropriately account for factors that vary with time across the study (i.e., training adherence). To control for Type-1 error rates cognitive outcomes will be tested using a Global Cognition Score (see 2a.3.i. Measures). Through randomization, we anticipate that the groups will be comparable in terms of demographic characteristics, premorbid intelligence, cognitive impairment, Axis-1 disorders, treatment participation, prescription medication use, training adherence and AUD and PTSD symptom severity. If significant differences exist, as indicated by Chi Square and t-tests, we will statistically adjust for these effects via inclusion as covariates in the analyses. We will conduct both a per protocol analysis on subjects who complete a minimum of 30 hours of training, and an intent-to-treat analysis on all randomized subjects, and report any differences in retention rates between the two conditions. For all models, variation inflation factors and tolerance will be obtained to assess for collinearity concerns. To account for family wise error, alpha will be adjusted in all secondary and exploratory analyses.

Stage 2, Aim 2 Hypotheses 1a - b. Participants who receive cognitive training as compared to those receiving a computer-game control training, will demonstrate at 6 month post-training follow-up: Aim 2 Hypothesis a (Primary): greater improvements in cognitive outcomes (Global Cognition Score); Hypothesis b (Secondary): reduced alcohol consumption (drinks per drinking day) and PTSD symptoms (PCL-M) and improved quality of life outcomes (DUQLS, IPF). In order to test these hypotheses, a series of 5 multiple linear regression tests will be conducted to assess the effect of condition on each primary outcome. Step 1 will include the baseline level of the primary outcome. Condition (intervention, control) will be entered on Step 2. Step 3 will include any necessary covariates (described above in *Planned Data Analyses*) to determine if effects still remain. From this model we will be able to estimate the covariate and baseline adjusted mean changes, and 95%CIs, in global cognition, alcohol use, PTSD and quality of life outcomes 6 months posttraining. Secondary analyses. Planned secondary analyses will mirror the above description for primary analyses. First, to follow-up the analysis with global cognitive functioning, we will explore the effects of cognitive training on targeted cognitive domains using individual Cognitive Domain Scores as outcomes. Second, although we expect gains observed in the cognitive training group to be sustained throughout the follow-up period (i.e., persistence of neuroplasticity based cognitive training benefits), we will determine whether the Global Cognition Score changed from post-training to follow-up. This statistical approach is more dismantled and therefore more specific, and offers several advantages over repeated measures ANCOVA.

Stage 2, Aim 2a Exploratory Hypothesis. Changes in global cognition will be significantly associated with decreases in alcohol consumption, PTSD symptom severity and increases in quality of life outcomes. Change scores will be computed for the Global Cognition Score, average drinks per drinking day, the PCL-M and the DUQLS and IPF, by computing the difference between follow-up and baseline. Four Pearson correlations will be performed to test associations between composite index change scores for Global Cognition and the 4 recovery outcomes. Exploratory Mediation and Moderation. We will explore potential mediators (i.e., training adherence and performance) and moderators (i.e., AUD and PTSD severity; Alcohol Use) of the effects of training condition on cognitive outcomes. The MacArthur approach to moderation and mediation analysis (Kraemer et al., 2008) will be employed. These analyses are considered exploratory

because, although the study is powered to detect main effects, we will have power to detect only very strong interaction and mediating effects.

2a.3.k. Timeline for Primary and Secondary Research Activities (See Table 3).

Primary Research Activities. During the start-up phase (months 1-3) of the proposed work, we will coordinate recruitment procedures with the outpatient SUD treatment program, finalize and purchase assessment and training tools and train study personal in the study protocol. A recruitment goal of 4 eligible participants per month was chosen based on prior experiences of the mentorship team who agreed that the goal was realistic and sufficient to meet study objectives, and to allow adequate time to conduct follow-up assessments. Recruitment for Stage 1 will start month 4 and last for 5 months. The weekly and post-training assessments for Stage 1 will be completed in month 9 and 3 month follow-ups will be completed in month 12. We will reserve time during months 13 and 14 to incorporate feedback from Stage 1 to refine the protocol and optimize feasibility for Stage 2. Stage 2 recruitment will begin at month 15 and will last until approximately month 46-47. Therefore, including start-up and Stage 1, all data should be collected by the *middle of year 5*.

Secondary Research Activities. In addition to the primary research activities outlined above and the training activities outlined below, I will also engage in manuscript writing, grant writing, and dissemination to further bolster my research program. Throughout the proposed award I will publish at least 4 manuscripts with members of my training team (using the existing prospective datasets they have made available to me) that examine cognitive mechanisms in SUD and PTSD. Publications will include the following topic areas: (1) cognitive influences on the relation between PTSD and AUD (Drs. [name], [name]); (2) prospective evaluation of cognitive influences on treatment outcomes in SUD, PTSD and SUD-PTSD (Drs. [name], [name], [name]); (3) contribution of impulsivity and related cognitive processes across addictive behaviors ([name]); (4) an integrative review of neurocognitive deficits observed in AUD and PTSD (Drs. [name], [name]). These projects will serve to inform cognitive screening procedures for Veterans entering SUD treatment that could be implemented to aid clinicians in treatment planning and delivery. This research in conjunction with initial CDA-2 data will also aid in the development of VA Investigator Initiated Research (IIR) grant. Specifically, beginning in the second half of year 4 I will develop a grant that proposes a larger-scaled randomized controlled clinical trial of mobile-based cognitive training for dually diagnosed SUD patients (e.g., SUD-PTSD). The primary aim of this grant is translational in nature. It will use data collected on malleable cognitive functions identified and therapeutically targeted in the proposed CDA-2, to generalize beyond AUD to other vulnerable SUD populations with complex comorbidities and across different VA treatment programs. In collaboration with operations partners (PERC, [name], SUD-QUERI, [name]), this research will also assess implementation and cost factors associated with cognitive training. Year 5 will be dedicated to revision and resubmission of the IIR and dissemination of findings via publications and presentations.

Table 3. Study Timeline.

Primary Activities	Year 1	Year 2	Year 3	Year 4	Year 5
Month	1 3 6 9 12	15 18 21	1 24 27 30 33	36 39 42 45 4	8 51 54 60
Start-up					
Stage 1:					
Baseline					
Training					
Follow-up					
Incorporate Feedback					
Stage 2:					
Baseline					
Training					
Follow-up					
Data Analyses					
Secondary Activities					
Manuscript Writing					
Grant Writing					
Dissemination

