As shown in Figure 1, 4 key domains of neurocognitive disruption in AUD/PTSD have been identified for remediation based on the literature reviewed. First, pre-existing cognitive biases to preferentially attend and respond to alcohol-related and threatening stimuli may be lessened with training. This should reduce the strength of triggers and expected rewards and help decrease the likelihood of potent habitual responses (i.e., alcohol-seeking, escape and avoidance behaviors). Second, improvement of attention, working memory and verbal and visual memory is expected to strengthen higher-order cognitive control processes and increase cognitive efficiency. In turn, this will help increase capacity to recognize situations and track cues that signal a potential threat to recovery goals. Third, training of response inhibition and targeting of delayed reward discounting should help to reduce the processes that lead AUD/PTSD individuals to discount future rewards (improved quality of life) in favor of immediate rewards (avoidance, drinking) and result in suboptimal decision making. Remediation of disruptions in this domain will increase the likelihood of temporarily withholding impulsive, stereotypic and overlearned responses and making decisions that factor in long-term consequences. Fourth, increased mental flexibility will equip individuals with enhanced executive control to shift attention away and identify and employ novel, flexible and adaptive strategies. This will help individuals

plan and sequence steps to align behavior more closely with recovery goals. Taken together, we predict that these improvements in cognitive functioning will directly (1) increase patients' ability to self-regulate emotions and behavior, (2) decrease alcohol seeking and use, (3) decrease PTSD symptoms and (4) enhance capacity to effectively implement more adaptive self-management strategies that will ultimately improve quality of life.

Figure 1. Conceptual model for the effects of cognitive training on cognitive functioning and recovery.

Neuroscience-Based Cognitive Training: Implications for AUD and PTSD

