- (2b) Studies with AUD populations have tended to target either cognitive biases or executive cognitive functions (e.g., working memory) but not both (as is proposed). Given the complicated nature of these conditions, simultaneous targeting of these core neurocognitive processes is important as they do not appear in isolation among affected individuals. The proposed research therefore represents a novel and important first step in translating basic laboratory research into intervention as no previous study has simultaneously and comprehensively targeted PTSD and AUD pathology with neuroscience-based cognitive training.
- (2c) The proposed study will address a tendency in the literature to create functional boundaries between different SUD research methods, by employing a multi-modal assessment of primary outcomes. Four levels of measurement will be incorporated: structured interviews, self-report measures, standardized

neuropsychological test batteries, and computerized behavioral tasks. This multi-modal assessment will function as a translational, integrated framework to demonstrate how measures of cognitive functioning, spanning from the neurocognitive to the self-report level, correspond in this population.

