The fifth_design consideration involved the "dose" of cognitive training to be administered. Previous research in schizophrenia populations has demonstrated that a signal may be detected at 20 hours (Keefe et al., 2011) though prolonged benefits (i.e., enduring cortical changes) require longer training periods (e.g., 50-80 hours; [name] et al., 2012). Cognitive training studies among AUD populations have employed highly variable training durations (2-20 hours) and schedules (4 to 25 sessions) and this variability appears to be driven by the nature of the exercises and the number of cognitive processes targeted (Fals-Stewart & Lam, 2010; Goldstein et al., 2005; Houben et al., 2011a; Rupp et al., 2012; Schoenmakers et al., 2010). Based on the training durations and associated gains previously observed in AUD populations (e.g., Bates et al., 2013), as well as the number of domains to be targeted and the associated exercises we will employ, we chose 30 hours as an optimal dose of training in the current study. Thirty hours will permit us to deliver approximately 7.5 hours of training targeting each of the 4 general cognitive domains illustrated in Figure 1 above.

The sixth design consideration was not to power the Stage 2 sample size to test whether change in cognitive outcomes mediates the relation between cognitive training (vs. computer game control) and recovery outcomes. Based on the early stage of research development ("Stage 1b efficacy"), we decided that powering the sample size for tests of mediation is not feasible or within the scope of the proposed research.

The seventh and final design consideration involved the decision to include individuals with comorbid Axis-I disorders (except Psychotic Disorders and Schizophrenia). Importantly, because AUD and PTSD are highly comorbid disorders, findings from the proposed study would dramatically suffer from limited generalizability should individuals with comorbidities be excluded from participation. Instead, Axis-I disorders and non-alcohol SUD will be comprehensively assessed and if necessary, controlled for if randomization procedures do not evenly disperse participants with comorbidities across conditions.

2a.3.b. Study Settings

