We will use a suite of BrainHQ exercises specifically designed to target and ameliorate disruptions in the 4 general domains described in Figure 1. We will employ basic exercises that focus on increasing processing efficiency in the auditory and visual perceptual and working memory domains, as well as exercises that target impulsivity and cognitive biases. Exercises will be packaged into 4 modules (attention skills, memory skills, executive functioning skills, cognitive control skills) comprised of 4 exercises each. All participants will progress through the same fixed schedule of modules. In each module of training, participants must improve the speed and accuracy of their responses in the targeted cognitive domain of interest. Participants are rewarded on correct trials with points and animations for their performance. Exercises continuously adjust difficulty level to user performance to maintain an approximately 80% correct performance rate. This "Bayesian adaptive" approach, in which the stimulus level at each trial is determined by the participant's responses from all previous trials, determines the level of maximum training efficacy. Compliance and performance will be monitored by data upload following each training session.

Computer Games Control Condition: Participants will play a rotating set of commercial computer games (see Appendix) at the same dose and frequency as the cognitive training. We selected this control activity because it mirrors the game-like properties of the cognitive training and it will be used to control for contact with research personnel and for the non-specific effects of participant motivation and engagement with daily computerized activities. It also allows for a double blind study design. Games from the website Sporcle.com will be used and an online account can be created for each participant. This feature allows the research team to track compliance and progress on the assigned computer games. This approach has been successfully used as a rigorous control condition for computerized cognitive training studies in schizophrenia (e.g., Fisher et al., 2009, 2010; Keefe et al., 2011) and is currently being employed in [name] (consultant) cognitive training study of Veterans with PTSD. The Sporcle.com computer games require low cognitive demand, and based on previous studies, are not anticipated to affect cognitive performance in the proposed training domains.

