Questionnaires. The cognitive training acceptability measure is comprised of a 22-items used by Posit Science to evaluate acceptability for their cognitive training software, and from components of a measure used by [name] research team. Items specifically assess user experience and satisfaction with the program, the web-based administration and the training schedule. The Computer System Usability Questionnaire (Lewis, 1995) will be employed to further assess usability. The 19-item CSUQ asks participants to rate the ease of usability, satisfaction, and enjoyability of a computer program.

Measures: Cognitive Functioning. The proposed neuropsychological test battery was carefully selected to assess the cognitive domains targeted for training and incorporates widely-used, standardized, well-validated and reliable measures. To minimize practice effects, alternative test forms will be used for repeated test administrations whenever feasible. The battery (see Table 1) will take approximately 2 hours, including allowances for breaks. Neuropsychological test data will be scored based on standardized age and, when available, educational and other demographic norms, and transformed into z scores for consistency. Specifically, raw scores on individual tests will be converted into z scores based on tables mapping normative

population data to optimal Gaussian distributions. A single Global Cognition Score (GCS) will be calculated to assess the impact of training on global cognitive functioning so as to reduce the variability and number of multiple comparisons. Specifically, *z* scores for tests within each domain will be summed and averaged to yield 4 Cognitive Domain Scores which will be summed to produce a single GCS (Strauss et al., 2006).

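### Cognitive bias is a named training target, but its only measure is analysed solely inside an average with three processing-speed tests, so no planned result can be attributed to bias

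*Combined protocol and SAP*

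**What the plan says.** **Bias as a target.** Section 2a.1, A Conceptual Model for Cognitive Remediation in AUD/PTSD, names four domains for remediation and begins with bias: "First, pre-existing cognitive biases to preferentially attend and respond to alcohol-related and threatening stimuli may be lessened with training". Attention comes under the second domain, together with memory. Section 2a.3.h, Computerized Cognitive Training, describes perceptual and working-memory exercises, "as well as exercises that target impulsivity and cognitive biases". Item 2b of the limitations part of section 2a.1 bases part of the study's novelty on this pairing: earlier AUD studies tended to "target either cognitive biases or executive cognitive functions (e.g., working memory) but not both (as is proposed").

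**Measurement and scoring.** Section 2a.3.i describes Approach Avoidance Tasks with alcohol-related and threatening stimuli. In Table 1 this is the only entry whose function is "Attentional and Cognitive Biases". It shares the domain Basic Attention and Cognitive Bias with Trail Making A, Symbol Search and Digit Symbol, which are listed under visuomotor attention and processing speed. The scoring rule is that "scores for tests within each domain will be summed and averaged to yield 4 Cognitive Domain Scores", and these are summed to the Global Cognition Score.

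**Analysis.** Under section 2a.3.j the primary cognitive outcome is the Global Cognition Score. The follow-up analysis is that "we will explore the effects of cognitive training on targeted cognitive domains using individual Cognitive Domain Scores as outcomes". The exploratory correlations use change in the Global Cognition Score. No analysis of the Approach-Avoidance Task alone is planned.

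**The concern.** The secondary analysis is meant to show which targeted domains responded to training. The score it uses for bias merges the model's first target with the attention part of its second. Bias supplies one of four components, or two of five if alcohol and threat are scored separately. The other three measure something else and can be expected to correlate with one another.

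This score can therefore move because processing speed improved while bias did not, and it can stay nearly still although bias improved. In either case the reader could not tell what happened to bias. At stake is whether the trial yields a pre-specified answer about a target that is central to its rationale and its novelty claim. The primary test is not at stake.

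**Working it through.** **The plan's own figure.** Section 2a.3.j states 80% power for d = .60 with 90 analysed, two-sided alpha .05, two-sample t-test. With 45 per arm, df = 88 and noncentrality .60 × √(45/2) = 2.85, the exact power is 80.4%. Attrition also agrees: 128 × .70 = 89.6, about 90. The stated sample size reproduces, and the same test is used below.

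**Inputs.** From the documents: 45 per arm, d = .60, two-sided .05, equal-weight averaging of z scores, three speed tests and the bias task in one domain. Assumed, because the documents give no correlations: r_s = .4 to .6 among the speed tests and r_b = 0 to .2 between bias and speed. If there are two bias scores, they are assumed to correlate .3.

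**Bias entered as one score (weight 1/4).**
- Variance of the mean of four unit-variance scores: (4 + 6r_s + 6r_b)/16.
- Lowest: (4 + 2.4 + 0)/16 = .40, SD .632. Highest: (4 + 3.6 + 1.2)/16 = .55, SD .742.
- Bias-only effect: mean shift .60/4 = .15, so d = .15/.742 to .15/.632 = .20 to .24.
- Speed-only effect: mean shift 3 × .60/4 = .45, so d = .45/.742 to .45/.632 = .61 to .71.

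**Alcohol and threat bias entered as two scores (weight 2/5).**
- Variance: (5 + 6r_s + 12r_b + 2 × .3)/25, so SD .566 to .681.
- Bias-only effect: mean shift 2 × .60/5 = .24, so d = .35 to .42.
- Speed-only effect: mean shift 3 × .60/5 = .36, so d = .53 to .64.

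| Scenario | d on domain score | Power |
|---|---|---|
| One bias score, bias-only d = .60 | .20–.24 | 16–20% |
| One bias score, speed-only d = .60 | .61–.71 | 81–92% |
| Two bias scores, bias-only d = .60 | .35–.42 | 38–51% |
| Two bias scores, speed-only d = .60 | .53–.64 | 70–85% |

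**Wider correlations** (r_s up to .7, r_b up to .3). With one bias score, power becomes 15–20% for bias only and 76–92% for speed only. With two, bias-only power becomes 34–51%. In every case the speed-only effect has much the higher power.

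**Bias analysed alone.** For d = .60 with 45 per arm, power is 80% at alpha .05, 71% at .025, 62% at .0125 and 59% at .01.

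**The case against.** **The four domain scores might follow the conceptual model, so that bias already has its own score.** The text speaks of four domain scores, while Table 1 as read shows five row labels, so the mapping of tests to domains does need clarifying. But section 2a.3.i, Cognitive Impairment, computes a deficit score from the screening tests for each of four domains in Table 1. The Approach-Avoidance Task is not a screening test, so a bias-only domain would have no such score. The descriptive text of section 2a.3.i also groups bias with basic attention, independently of the table layout. Bias shares its domain whether four or five scores are meant.

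**Aggregation is deliberate.** It is justified as limiting variability and multiple comparisons. That supports the primary Global Cognition Score, which needs no change. It is not a reason to merge two constructs in an analysis meant to explore targeted domains.

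**The design already accepts that components cannot be separated.** The third design consideration in section 2a.3.a concedes this for training modules. Whether the whole package changed bias is a different question, and the randomised comparison can answer it.

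**The figures depend on the scenario.** This stands. The correlations are assumed, the contrast takes no effect at all on the other component, and the calculation uses neither the planned baseline adjustment nor the adjusted alpha. The plural Tasks in section 2a.3.i may mean two bias scores, which lessens the dilution.

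**Training time.** A reader might set the small weight of bias against a quarter of the training, since section 2a.3.a gives "approximately 7.5 hours of training targeting each of the 4 general cognitive domains". The documents do not confirm that share. Figure 1 is not shown, and the four modules in section 2a.3.h are attention, memory, executive functioning and cognitive control, none of them a bias module.

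**Conclusion.** The point holds as a gap in the secondary analysis. A significant score for Basic Attention and Cognitive Bias could not be attributed to bias, and a non-significant one could not exclude a bias effect. This attribution problem follows from the scoring rule and does not depend on the assumed correlations. The power figures do: a bias-only d = .60 has about 16–20% power with one bias score, or about 34–51% with two over the wider range. A speed-only d = .60 has about 81–92% with one.

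Two stronger readings are not supported. A reader might infer that the trial will report a wrong conclusion about bias. But the plan states no separate bias hypothesis, and the domain label openly names both constructs; what is missing is a pre-specified answer. A reader might also infer that a bias effect would be practically undetectable. With two bias scores, power could reach about half. The primary hypothesis and the sample size are not affected. I would treat this as a cheap improvement.

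**What to change.** Keep the Global Cognition Score as planned. In the secondary analyses of section 2a.3.j, split this domain in two:

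- an attention and processing-speed score from Trail Making A, Symbol Search and Digit Symbol;
- a bias score from the Approach-Avoidance Task, stating whether alcohol and threat are analysed separately or combined, and which direction of scoring means improvement.

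Regress each on its own baseline and condition, within the alpha-adjusted secondary family, and draw conclusions about bias only from the bias score. In the same edit, state which tests form each of the four domain scores.

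The cost is a change of wording and one or two more secondary tests. The task is already in the battery. The post-training and follow-up battery is described as abbreviated without listing its tests, so the plan should confirm that this task is retained. The added tests also have a price in power: for d = .60 on bias with 45 per arm, about 71% at alpha .025 and 59% at .01, short of 80%. That still exceeds the power of the planned domain score for a bias-only effect at unadjusted .05.
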